7.4.4 Analysis of Immunogenicity Variables

T-cell responses to pp65 and gB-specific antibody levels will be summarized by visit and treatment group on the original scale. A plot of each of the immune responses over time by treatment will be produced. The comparisons between treatments will be made at each measurement visit using Wilcoxon rank sum test without adjusting for the multiplicity on the original scale. In addition, each of the immune response variables post baseline on the 10 based log scale will be analyzed using repeated measures model, where the randomization stratum, treatment, time, and treatment by time interaction will be the explanatory variables. The self-consistent sandwich correlation structure will be used. If the test for the time by treatment interaction is significant (p value<0.1) the overall treatment group comparison will not be displayed in the plots.

As an exploratory analysis, the relationship between immunogenicity variables and treatment outcome will be assessed using logistic regression method. The treatment outcome is if subject is free of CMV viremia through one year post-transplant. The optimal cutoff values of the respective immunogenicity variables that will define the treatment outcome will be explored in terms of maximizing the area under the receiver operating characteristic (ROC) curves.

All analyses of immunogenicity variables will be based on the IAS.

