7.4.4 Immunogenicity Analysis

T-Cell responses to pp65 and gB-specific antibody levels will be compared at each time point using the Wilcoxon rank-sum test. Graphic presentation of the mean of T-Cell responses to pp65 and gB-specific antibody levels over time by treatment group will also be provided.

Immunogenicity analysis will be performed using the FAS.

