17. Concomitant Medication Restriction or Requirements, Prohibited Concomitant Medications (Drugs and Therapies)
DESCRIPTION OF CHANGE:
Revise wording for Alemtuzumab and Rituximab as well as adding additional prohibited medications. Also clarify time periods for prohibited medications.
RATIONALE:
Alemtuzumab (T cell depleting agent), ATG (T cell depleting agent) and anti-CD 20 antibodies (B cell depleting agent) may interfere with effectiveness of the vaccine. Therefore, if a subject is planned to receive any one of these agents through the primary study period they are excluded. However, it is not ethical to prevent subjects from receiving these agents if they are clinically indicated, and, to prevent protocol violations and drop-outs,

subjects may receive these agents if clinically indicated after they have been Randomized into the trial.
18. Concomitant Medication (Drugs and Therapies)
DESCRIPTION OF CHANGE:
Clarify that the medications used for anesthesia during the transplant will not be recorded.
RATIONALE:
To clarify procedures other than the transplant using anesthesia must have those anesthetic agents recorded. Medications used for anesthesia are difficult to record and are not expected to affect the outcome of the trial.
19. Concomitant Medication Restriction or Requirements, Prohibited Concomitant Medications (Drugs and Therapies)
DESCRIPTION OF CHANGE:
Insert wording to note that IVIG and plasmapheresis are not allowed from Day of Transplant through the Day of Randomization.
RATIONALE:
IVIG and plasmapheresis significantly suppress immune responses and, therefore, are likely to interfere with the efficacy of the vaccine.
20. Discontinuation Criteria
DESCRIPTION OF CHANGE:
Clarify wording to reflect that grading should be confirmed by a health care professional's (HCP).
RATIONALE:
To specify that grading > 3 as assessed by the subject, must be confirmed by a HCP.
21. Discontinuation Criteria
DESCRIPTION OF CHANGE:
Add anaphylaxis as discontinuation criteria.
RATIONALE:
Anaphylaxis of Grade ≥ 3 per NCI Criteria warrants discontinuation from the study.
22. Endpoints for Evaluation; Exploratory Endpoints
DESCRIPTION OF CHANGE:
Simplify the language of Healthcare utilization to be recorded.
RATIONALE:

Previous language and data to be collected were duplicate data and clarification given on how to record inpatient and outpatient days.
23. Flow Chart and Schedule of Assessments
DESCRIPTION OF CHANGE:

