3.2 Study Design

This is a randomized, double-blind, placebo-controlled trial which will enroll 140 CMV-seronegative recipients of kidney transplant from a CMV-seropositive donor at about 80 clinical sites. Subjects will be randomized at Day 30 \pm 3, in relation to the day of transplant, in a 1:1 ratio to ASP0113 or placebo, and stratified by use of anti-thymocyte globulin (ATG) prior to Randomization and by receipt of a kidney from a living or deceased donor. The active compound will be a vaccine (ASP0113) which contains two plasmids encoding gB and pp65 each at 2.5 mg/mL, formulated with CRL1005 poloxamer and benzalkonium chloride (BAK).

The placebo control will be phosphate-buffered saline (PBS). Subjects will receive either 5 doses of ASP0113 or placebo on Days 30 \pm 3, 60 \pm 5, 90 \pm 5, 120 \pm 5 and 180 \pm 5 in relation to the day of transplant (Day 0).

Injections should be administered only when there is no medical contraindication to an intramuscular (IM) injection. Syringes will be masked prior to dosing to blind the subjects and all other personnel who need to remain blinded to the treatment assignment (i.e., site staff other than pharmacy personnel and staff designated to administer Study Drug injections).

Starting within 10 days of transplant, subjects will have received prophylactic valganciclovir or ganciclovir (dose per package insert) through the day of Randomization to prevent CMV disease. (The subject can miss up to two valganciclovir or ganciclovir doses during this time period for any reason). Subjects will then continue to receive CMV specific CMV AVP with valganciclovir or ganciclovir (dose per package insert) to prevent CMV disease until 100 days post transplant. Subjects can have valganciclovir or ganciclovir interrupted, dose adjusted or replaced by other CMV-specific AVP per standard of care after the day of Randomization if renal function is compromised, there are toxicities related to the administration of the AVP or for any other medically indicated reason. In all subjects, plasma will be collected for central laboratory CMV viral load testing every two weeks from Day 100 through Day 200, then monthly through last Study visit Day 395.

In cases where CMV disease (CMV syndrome or CMV tissue-invasive disease) is suspected from the first Study Drug injection through Day 395, a local CMV viral load sample will be collected at the time of the first CMV symptom recognition.

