Classifications of opportunistic infections other than CMV: Any TEAE with the following classifications will be considered and decided by the medical and safety officers of the study team before unblinding case by case if it is an opportunistic infection: (1) SOC: Renal and Urinary disorders and HLGT= Viral infectious disorders, Chlamydial Infections disorder, Mycobacterial infectious disorders, Fungal infectious disorders, Bacterial infectious disorders, Protozoal infectious disorders; (2) SOC: Renal and Urinary disorders and HLT= Genitourinary tract inflammation and infection NEC, Bladder infections and inflammations, Renal infections and inflammation, Urethral infections and inflammations.

Count episodes of the protocol defined CMV viremia:

An episode starts with CMV viral load ≥ 1000 IU/mL by central assay and ends with two consecutive CMV viral load < 1000 IU/mL by central assay separated by at least one week in time. An episode will not be counted if it starts outside the primary study Period.

The ordinal variables below assessed by the central laboratory will be compared between treatments using the stratum-adjusted Wilcoxon rank-sum test. This test is implemented in SAS Proc Freq using the CMH2 option for tests based on row mean scores and SCORES=MODRIDIT option for use of modified standardized rank score within strata:

- Peak CMV viral load
- Cumulative viral load

Calculation of cumulative viral load:

Using the linear trapezoidal rule to calculate the area under the viral load over time curve (AUC) divided by the length of time for each subject.

The eGFR and its change from baseline will be summarized by treatment at each visit and at final visit. The change from baseline to final visit will be compared using analysis of

covariance (ANCOVA) with treatment and randomization stratum as factors and baseline value as a covariate.

Calculation of eGFR:

$$186 \times \text{serum creatinine}^{-1.154} \times \text{age}^{-0.203} \times [1.212 \text{ if Black}] \times [0.742 \text{ if Female}] ,$$

where serum creatinine is in mg/dL and age in years. The value in either bracket is 1 if the stated condition is not met. If serum creatinine is in SI units (mmol/L) instead of the US units (mg/dL) then its value needs to be converted to the US units first by multiplying a factor of 1/88.4.

Data from KTQ and SF-12 will be listed without any analysis.

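### The by-visit Wilcoxon tests of pp65 T-cell and gB antibody levels ignore the randomization strata; the stratum-adjusted version already in SAP 7.4.3 would be a cheap, low-severity improvement

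*SAP*

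**What the plan says.** For the two immune markers, SAP 7.4.4 specifies on the original scale: "The comparisons between treatments will be made at each measurement visit using Wilcoxon rank sum test". No stratum appears in that sentence. Protocol 7.4.4 is the same: the markers "will be compared at each time point using the Wilcoxon rank-sum test".

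The surrounding text treats the strata differently:

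- SAP 3.2: subjects are "stratified by use of anti-thymocyte globulin (ATG) prior to Randomization and by receipt of a kidney from a living or deceased donor", which gives four strata.
- SAP 7.4.3: peak and cumulative viral load are compared between "treatments using the stratum-adjusted Wilcoxon rank-sum test", implemented through CMH2 with modified ridit scores. Protocol 7.4.3 had a plain Wilcoxon here too, so the SAP upgraded one rank comparison and left the other.
- SAP 7.4.4, immediately after the by-visit test: the log10 responses are also analysed in a "repeated measures model, where the randomization stratum, treatment, time, and treatment by time interaction will be the explanatory variables".
- Protocol Attachment 1, rationale for substantial change 17: "ATG (T cell depleting agent") is listed among agents that might interfere with the vaccine.

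Neither SAP 7.4.4 nor the list of changes in SAP Appendix 4 explains the different handling.

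**The concern.** Stratified randomization balances the strata between arms by design. A rank test that pools the strata still counts between-stratum spread as noise. If the strata predict the outcome, its nominal variance is too large: it rejects too rarely under the null and loses power under the alternative.

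ATG is a plausible predictor of a T-cell read-out. SAP 6.1.4 names a rise in the two markers relative to placebo as the indicator of immunogenicity. The by-visit comparisons will therefore help readers judge whether the vaccine was immunogenic in immunosuppressed recipients. What is at stake is some sensitivity in that supportive read-out.

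**Working it through.** **The plan's own figure.** The documents state no power for the immune comparisons. The only sample-size figure, 64 per arm for viremia of 46% against 25% (1-sided 5%, 80% power), reproduces: n = 64, power 80.5%. It does not bear on this point.

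**Inputs from the documents.** 1:1 allocation; 70 per arm enrolled (N = 140); four strata; 1-sided 0.05, which SAP 7.1 states for efficacy comparisons.

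**Assumed inputs.** Normal response with within-stratum SD 1; vaccine shift 0.43 SD (about 80% power at N = 140); ATG share 30% or 50%; 60% deceased donors; no donor-type effect; ATG effect *b* from 0 to 1.5 SD; N = 140, or 100 to allow for samples not available.

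**Test statistics.** Plain test: pooled ranks. Adjusted test: scores rank/(n_k + 1) within stratum k; sum over strata of (vaccine score total − m_k × mean score), divided by the square root of the sum of s_k² m_k(n_k − m_k)/n_k. Here n_k is the stratum size, m_k the vaccine subjects in it and s_k² the variance of its scores.

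**Hand approximation, N = 140.** With ATG share *p*, the pooled SD is inflated by k = √(1 + p(1 − p)b²), so the effective critical value is 1.645k. The signal is 0.43 × √140/2 × √(3/π) = 2.486. For p = 0.5:

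- b = 0: k = 1, power Φ(2.486 − 1.645) = 80.0%.
- b = 1: k = √1.25 = 1.118, critical value 1.839, size 3.3%, power Φ(0.647) = 74.1%.
- b = 1.5: k = √1.5625 = 1.25, critical value 2.056, size 2.0%, power Φ(0.430) = 66.6%.

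**Simulation, 10,000 trials per setting.** Plain → adjusted power, with the plain test's null rejection rate in brackets:

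| ATG effect (SD) | N=140, 30% ATG | N=140, 50% ATG | N=100, 30% ATG | N=100, 50% ATG |
|---|---|---|---|---|
| 0 | 80.1 → 79.4 (5.0) | 80.3 → 79.5 (5.2) | 66.8 → 65.5 (4.9) | 66.8 → 66.0 (4.9) |
| 0.25 | 79.4 → 79.0 (5.2) | 79.2 → 78.9 (5.0) | 67.2 → 66.6 (5.2) | 66.1 → 65.8 (4.6) |
| 0.5 | 78.5 → 79.0 (4.6) | 77.3 → 78.2 (4.3) | 65.6 → 66.1 (4.6) | 65.0 → 65.8 (4.8) |
| 1.0 | 74.2 → 78.6 (3.6) | 74.3 → 79.6 (3.4) | 61.5 → 66.5 (3.4) | 59.5 → 65.9 (3.6) |
| 1.5 | 67.9 → 78.9 (2.2) | 64.3 → 78.7 (1.7) | 52.6 → 65.2 (2.6) | 49.7 → 66.1 (2.1) |

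The adjusted test's null rejection stays between 4.7% and 5.4%. The hand approximation agrees with the plain-test column to within about 2.5 points.

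A separate simulation with two strata, 60 per arm, a 0.45 SD shift and half the subjects on ATG (4,000 trials) gave 75.7 → 77.7% at 0.5 SD, 71.1 → 76.8% at 1 SD and 61.2 → 76.2% at 1.5 SD. The 2-point upper end at 0.5 SD comes from this run.

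**Assay floor.** The subjects are seronegative, so many values may tie at the bottom of the assay. With tied values at a floor (shift 0.5 SD, N = 140, 50% ATG), the adjusted test changes power by −0.3 to +1.2 points for an ATG effect of 0 or 0.5 SD, and by +3.0 to +5.0 points at 1 SD. A responder-type floor model with assumed responder rates (50 or 60 per arm, 4,000 trials) gave −0.6 to +1.6 points.

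**The case against.** The strongest reply is that the next sentence of SAP 7.4.4 already supplies a stratum-adjusted analysis of the same markers, with an interaction that lets the vaccine effect vary by visit. That stands: a reader might infer that the immune read-out as a whole is unadjusted, and it is not. The model is not a full substitute, though. The section does not promise by-visit contrasts from it. If the interaction has p < 0.1, "the overall treatment group comparison will not be displayed in the plots". The section also gives no rule for values that cannot be put on a log scale.

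Other objections also stand and limit the point:

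- A reader might infer that this is the only analysis that drops the strata. The log-rank analysis in SAP 7.4.1.2, reused in 7.4.3 for time to CMV disease, names none either.
- A reader might infer a large loss of power. No document gives an ATG effect on pp65 or gB or the share of subjects on ATG, so the double-digit figures rest on an assumed 1.5 SD effect.
- A reader might extend the ATG argument equally to gB antibody. The documents state only T-cell depletion and possible interference with the vaccine.
- A reader might infer that skipping T-cell samples at a lymphocyte count of 500 or below shifts the ATG mix between arms. The documents show no such drift. The rule could equally remove the most depleted subjects and shrink the ATG effect.
- These comparisons are unpowered, unadjusted for multiplicity, and neither primary nor secondary.

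**Conclusion.** The gap is real but small. The by-visit rank tests ignore strata that were used to randomize and that the SAP uses for its other rank comparisons. The tests remain valid; any error is conservative, with no false-positive risk.

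Under normal responses, the power given up is about 0 to 2 points for an ATG effect up to 0.5 SD, 4 to 6 points at 1 SD and 11 to 16 points at 1.5 SD. It is less where many values sit at an assay floor. Which of these applies cannot be settled from the documents. A reader might go further and infer that the primary result is compromised. It is not: the primary CMH test in SAP 7.4.1.1 is stratified by both factors and does not use these comparisons. Low severity; worth doing because it is nearly free.

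**What to change.** In SAP 7.4.4, replace the plain Wilcoxon with the stratum-adjusted Wilcoxon of SAP 7.4.3 (PROC FREQ, CMH2, SCORES=MODRIDIT), stratified by ATG use and donor type, at each immunogenicity visit. Keep the repeated measures model as it is. Record the change in SAP Appendix 4 before hard lock and unblinding.

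The cost is one sentence and the reuse of planned code, with no new data. If the strata do not predict response, the price is about 1 point of power (0.7 to 1.3 points in the settings above).

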Sites that are determined to have an unacceptable assay in their local lab but are able to determine a Sponsor- deemed acceptable work practice flow for utilizing another acceptable local assay or methodology will be allowed to participate in the trial. Note: Local CMV plasma viral load testing may be performed only at a local laboratory approved by the Sponsor.

Subjects will be followed for one year after first Study Drug injection (Primary Study completion/Day 395) for CMV viremia, CMV syndrome, CMV tissue-invasive disease, CMV-specific AVT, graft survival and subject survival.

Subjects will be followed for one year after the first Study Drug injection for resistance to valganciclovir or ganciclovir. Viral resistance will be assessed by a Central lab when there is no reduction in viral load two weeks after initiating valganciclovir/ganciclovir, when there is no improvement in clinical signs and symptoms two weeks after initiating valganciclovir/ganciclovir or any time resistance to any CMV-specific AVT is suspected by the Investigator.

Immunogenicity to pp65 and gB will be assessed prior to Dose 1, two weeks after Dose 2, prior to Dose 3, two weeks after Dose 4, prior to Dose 5 and at the last study visit.

Subjects will be evaluated for local and systemic reactogenicity 15 minutes and one hour after each Study Drug injection and for 7 days by subject reporting via diary after each Study Drug injection.

Subjects will be contacted by telephone at 6 months after Day 395, then annually for the next 4 years to evaluate long-term safety related to the DNA vaccine. Items to be assessed by questionnaire and available patient records include mortality, development of any new malignancies, development of infection requiring hospitalization or resulting in death, graft survival, creatinine, and erythema and/or induration at the injection sites (see Appendix 17).

All adverse events (AEs) and serious adverse events (SAEs) will be collected from signing of the informed consent through one year post Study Drug injection. AEs occurring from signing of informed consent until just prior to the first dose of Study Drug, should be reported as a change in medical status or medical history. SAEs from the time of signing the informed consent will be recorded on the SAE worksheet and reported per Section 5.5.6. AEs reported after the first dose will be reported on the AE eCRF. The transplant surgery that occurs on Day 0 is not considered an AE or an SAE.

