3.2 Inclusion Criteria

Subject is eligible for the study if all of the following apply:

1. Institutional Review Board (IRB)/Independent Ethics Committee (IEC)-approved written informed consent and privacy language as per national regulations (e.g., Health Insurance Portability and Accountability (HIPAA) Authorization for U.S. sites) must be obtained from the subject or legally authorized representative prior to any study-specific procedures (including withdrawal of prohibited medication, if applicable).
2. Subject is willing to comply with the protocol.
3. Subject is \geq 18 years of age or the legal age of consent (whichever is greater).
4. Subject is CMV-seronegative at time of transplant and has received a kidney allograft from a CMV-seropositive living or deceased donor. CMV serostatus of the recipient can be determined from 8 weeks prior to transplant, by local laboratory, through day of transplantation. If CMV serostatus is not available from this time period, CMV serostatus may be assessed at the Screening Visit, by local laboratory, with results available prior to Randomization.
5. Subject started valganciclovir or ganciclovir within 10 days of transplant and has received it through Randomization per regulatory label (package insert).
6. Female subject must be either:
 - Of non- child-bearing potential:
 - post-menopausal (defined as at least 1 year without any menses) prior to Screening, or
 - documented surgically sterile or status post hysterectomy (at least 1 month prior to Screening).
 - Or, if of childbearing potential:
 - must have a negative urine pregnancy test at Screening, and
 - if heterosexually active, must use two forms of birth control* (at least one of which must be a barrier method) starting at Screening and during the Primary Study Period.

7. Female subject must not be breastfeeding at Screening and during the Primary Study Period.
8. Female subject must not donate ova starting at Screening and during the Primary Study Period.
9. Male subject and their female spouse/partners who are of childbearing potential must be using highly effective contraception consisting of two forms of birth control* (one of which must be a barrier method) starting at Screening and during the Primary Study Period.

* Acceptable forms include:

- Established use of oral, injected or implanted hormonal methods of contraception.
- Placement of an intrauterine device (IUD) or intrauterine system (IUS).

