3.3 Exclusion Criteria

Subject will be excluded from participation if any of the following apply:

1. Subject is planned to undergo a course of CMV-specific prophylactic therapy with antiviral drugs with a duration of greater than 100 days.
2. Subject has received from one month prior to transplant or is planning to receive CMV immunoglobulin.
3. Subject has had CMV viremia or CMV disease from time of transplant until time of Randomization.
4. Subject has received, at any time, an organ transplant other than a kidney. (Dual allocation of a kidney is allowed).
5. Subject requires dialysis on the day of Randomization.
6. Recipient or donor is known to be positive for human immunodeficiency virus (HIV), hepatitis B surface antigen, or hepatitis B core IgM or IgG antibody.
7. Subject is known to have latent or active tuberculosis which has not been adequately treated.
8. Subject required desensitization for ABO blood type incompatibility or a positive T or B cell crossmatch.

9. Subject has received any of the following substances or treatments:
- a. Investigational therapy within 28 days or 5 half lives whichever is longer, prior to Transplantation, or subject is scheduled to receive investigational research products through one year after Randomization.
 - b. Alemtuzumab within 90 days prior to Randomization or is scheduled to receive alemtuzumab any time through one year post Randomization.
 - c. Rituximab within 120 days prior to Randomization or is scheduled to receive rituximab any time through one year post Randomization.
 - d. Eculizumab or bortezomib from the Day of Transplantation through the Day of Randomization or is scheduled to receive eculizumab or bortezomib any time through one year post Randomization.
 - e. IVIG and/or plasmapheresis from Day of Transplant through Day of Randomization.
 - f. Live attenuated vaccines within one month (30 days) prior to the first dose of Study Drug or is scheduled to receive live attenuated vaccines within one month of any Study Drug injection.
 - g. Subunit or killed vaccines within 14 days prior to the first dose of Study Drug or is scheduled to receive subunit or killed vaccines within 14 days of any Study Drug injection.
 - h. Administration of a CMV vaccine, including any prior exposure to ASP0113.

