16. Donor information includes donor demographics (age, gender, race), viral serologies (CMV [required], HBV, HCV, EBV, [if available]; and HCV PCR RNA [if available]), ABO blood group and HLA typing. Recipient information includes ABO blood group, HLA typing, HLA cross match at time of transplant (as determined by the site's standard method of determination), and viral serologies (CMV [required], HBV, HCV and EBV [if available], and HCV PCR RNA [if available]).
17. Plasma viral load by the central laboratory will be routinely monitored every other week (+/-3 days) from Day 100 through Day 200, then monthly (+/- 5 days) until end of study. Plasma viral load by central and local laboratory will also be assessed for cause in case of suspect CMV disease and at least once a week by Central lab from initiation of CMV-specific AVT until the course is completed. For cause CMV viral loads should be performed at a local lab approved by Astellas as Central lab viral load results may not be available in a timely manner to guide treatment decisions.
18. Plasma viral load assessment results performed by the local laboratory will be reported on the eCRF. Local CMV plasma viral load testing may be performed only at a local laboratory approved by the Sponsor.
19. A plasma sample will be drawn and sent to the central lab and results will be reported for CMV genotypic resistance when there is viremia without a reduction in viral load after two weeks of treatment with valganciclovir and/or ganciclovir, or when clinical signs and symptoms have not improved two weeks after initiating or increasing valganciclovir and/or ganciclovir for CMV viremia or disease or any time resistance to any CMV-specific AVT is suspected by the Investigator.
20. Immunogenicity laboratories include collection of blood for the gB antibody and pp65 T-cell assays. Samples should be drawn at Visits 2, 5, 6, 9, 10 and 13. Visits 2, 6 and 10 are Study Drug injection visits and blood sampling will be collected prior to the Study Drug injection. Samples for T-cell assays will not be collected if the Absolute Lymphocyte Count (ALC) is known to be $\leq 500 \text{ mm}^3$ by local or central laboratory measurement.
21. Subjects who consent to participate in the PGx sub study will have a whole blood sample collected during the Baseline Visit (Visit 2), after Randomization but prior to the first Study Drug injection.

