6.1.4 Immunogenicity Variables

An indicator of immunogenicity elicited by the vaccine is predicted to be an increase in gB-specific antibody levels and the T-cell response to pp65 protein over time compared with the placebo group.

Two immunogenicity assessments will be performed:

1. T-cell response to viral protein pp65 using cultured ELISpot .
2. Antibody response to gB antigen using an ELISA-based platform.

Assessments will be done from peripheral blood mononuclear cells (T-cells) or serum samples (antibody) isolated over the course of the trial. Time points of the assessments are as follows:

Dose 1, Post Dose 2, Dose 3, Post Dose 4, Dose 5, and End of Study Visit:

- Samples for T-cell assays will not be collected if the Absolute Lymphocyte Count (ALC) is known to be $\leq 500 \text{ mm}^3$ by local or central laboratory measurement.
- If the visit coincides with a study drug administration, the sample will be drawn prior to injection.

Further details will be available in the Laboratory Manual.

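### The supplementary repeated-measures immunogenicity model does not use the pre-dose Visit 2 value, giving up a probably small amount of precision

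*SAP*

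**What the plan says.** Immunogenicity is sampled six times. SAP 6.1.4 lists the time points as "Dose 1, Post Dose 2, Dose 3, Post Dose 4, Dose 5, and End of Study Visit". The first is a true pre-treatment value: the schedule footnotes in SAP Section 2 state that "Visits 2, 6 and 10 are Study Drug injection visits and blood sampling will be collected prior to the Study Drug injection", and Protocol 2.2.1 agrees ("Immunogenicity to pp65 and gB will be assessed prior to Dose 1").

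SAP 7.4.4 compares the arms at each visit by Wilcoxon rank-sum test on the original scale. It then adds a second analysis, a repeated-measures model of the log10 values taken after baseline. Its terms are set out as follows: "where the randomization stratum, treatment, time, and treatment by time interaction will be the explanatory variables". The Visit 2 value is not among the terms and, since only later values are modelled, is not in the outcome either.

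Four other provisions bear on the point:

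- SAP 7.4.3 compares eGFR change by ANCOVA with the baseline value as covariate.
- SAP 6.1.4 has no T-cell sample drawn when the absolute lymphocyte count is known to be 500 per mm³ or lower. The rule is not limited to visits after baseline.
- SAP 5.3 admits a subject to the Immunogenicity Analysis Set (IAS) on one post-transplant measurement and does not ask for a baseline.
- SAP 7.9.1 leaves missing values unimputed apart from the variables it names.

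**The concern.** SAP 6.1.4 describes the expected signal of immunogenicity as a rise over time relative to placebo. A rise is judged from a starting point. The starting value is collected by design, yet the only longitudinal model in the plan sets it aside. With 70 subjects enrolled per arm, and T-cell data further thinned by the lymphocyte rule, the arms may differ by chance at Visit 2, and the planned model has no term to absorb that.

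What is at stake is the width of the confidence intervals in one supportive analysis. Randomization keeps the comparison unbiased with or without the baseline.

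**Working it through.** **The plan's own figures.** The documents state no power, standard deviation or precision for the immunogenicity model. The only sample-size figure, 64 per arm (SAP Section 4), is for the primary endpoint. It reproduces: 46% versus 25%, one-sided 5%, 80% power, pooled variance and no continuity correction give 64 per arm, with power 80.5%. It does not depend on the immunogenicity model.

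**Gain at one visit.** Let r be the correlation between the log10 Visit 2 value and a later log10 value. Linear adjustment multiplies the residual variance by 1 − r². The documents give no r, so the values below are assumed. The equivalent gain in subjects is 70/(1 − r²) − 70. The power column starts from an illustrative comparison with 80% power at one-sided 5%.

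| assumed r | variance factor | SE factor | equivalent extra subjects per arm | 80% power becomes |
|---|---|---|---|---|
| 0.1 | 0.99 | 0.995 | 0.7 | 80.3% |
| 0.2 | 0.96 | 0.980 | 2.9 | 81.4% |
| 0.3 | 0.91 | 0.954 | 6.9 | 83.2% |
| 0.5 | 0.75 | 0.866 | 23.3 | 89.0% |

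**Which r is plausible.** Three eligibility rules push baselines towards the assay floor: "Subject is CMV-seronegative at time of transplant and has received a kidney allograft from a CMV-seropositive living or deceased donor" as an inclusion criterion, and as exclusions "Subject has had CMV viremia or CMV disease from time of transplant until time of Randomization" and "Subject has received from one month prior to transplant or is planning to receive CMV immunoglobulin". Values held at a floor correlate weakly with anything. This was simulated with bivariate normal log values and the baseline censored at the assay limit. With 2% to 10% of baselines above the limit and an underlying correlation of 0.3 to 0.7 (all assumed), the observed r was 0.09 to 0.36. Variance fell by 0.8% to 13.3% and the standard error by 0.4% to 6.9%. An r of 0.1 to 0.3 is therefore a fair working range. The 25% reduction at r = 0.5 needs baselines spread well above the limit.

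**Cost of a complete-case covariate.** If a fraction m of subjects has no baseline and is dropped, the variance factor becomes (1 − r²)/(1 − m). The gain is cancelled when m = r²: 1%, 4% and 9% missing at r = 0.1, 0.2 and 0.3. With an assumed m of 10%, r = 0.2 gives 0.96/0.90 = 1.067 and r = 0.3 gives 0.91/0.90 = 1.011. Both are worse than not adjusting. The documents do not give m for the T-cell assay.

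**The case against.** The strongest case for leaving the model alone has four parts.

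**Little to gain.** In a seronegative population the baseline is nearly constant. This largely stands and is why the point is small. It does not show a gain of zero. The Visit 2 sample comes about 30 days after a graft from a seropositive donor, whereas serostatus is normally fixed by the day of transplant. Scheduled central viral load testing starts only at Day 100 (Table 1a), so early replication is not systematically ruled out. Antibody serostatus also does not determine background in a T-cell assay.

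**A cost in subjects.** For T-cells a plain covariate would drop subjects with low lymphocyte counts and change who is analysed. This stands against that form of adjustment only. Forms that retain these subjects avoid it.

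**The formula is for one visit.** The model has five post-baseline visits over a year, and a single common slope need not yield 1 − r² at each. This stands, and the figures above should be read per visit.

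**Little depends on it.** Protocol 7.4.4 plans only Wilcoxon tests and graphs. The model is an addition, without multiplicity control or a sample size, and the by-visit summaries would show a baseline imbalance. This also stands, although seeing an imbalance does not adjust for it.

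A reader might also infer that the SAP is inconsistent because it adjusts eGFR for baseline. That goes too far. The eGFR outcome is change from baseline, which already requires a baseline, so the covariate there costs no subjects. Treating a post-baseline level differently is defensible.

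**Conclusion.** The omission is real, and using the Visit 2 value would be a valid, minor improvement to a supportive analysis. On an assumed correlation of 0.1 to 0.3, variance at a single visit falls by about 1% to 9%, equivalent to roughly 1 to 7 extra subjects per arm at 70 enrolled. The estimate rests on that assumed correlation and on most baselines lying near the assay floor. Neither is reported in the documents.

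Two stronger readings are tempting. One is that the plan gives up free precision with no downside. The documents do not support it: the lymphocyte rule, the absence of imputation and an IAS that needs no baseline mean that the simplest adjustment can lose more than it gains. The other is that the T-cell gain would be substantial, 25% or more. Nothing in the documents on baseline spread, assay limit or correlation shows this.

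**What to change.** Before unblinding, amend SAP 7.4.4 so that the log10 Visit 2 value enters the model in a form that keeps every IAS subject with a post-baseline value. Either of these would do:

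1. **Constrained longitudinal model.** Put Visit 2 in the outcome vector with one baseline mean common to both arms. The adjustment works through the estimated correlation between visits, so specify a likelihood fit with an unstructured covariance. A working-independence fit would bring no gain.
2. **Covariate with indicator.** Add the Visit 2 value as a covariate, with a fixed fill value where it is missing and a missing-baseline indicator. A baseline-by-visit term can be added if the slope is expected to change over the year.

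In either form, set values below the assay limit to a stated constant, and state that a complete-case covariate will not be used. The cost is slightly more modelling work and a few lines of text. No new data are needed, and the per-visit Wilcoxon tests stay as they are.
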